# 2.4.2. Obesity surgery as a novel way for studying the causes and consequences of obesity

Over the past decade, bariatric weight loss surgery has gained increasing acceptance as a treatment modality for morbid obesity. Bariatric surgery is a very effective means for weight loss among morbidly obese patients. Surgical treatment results in pronounced weight loss in short time and has also beneficial effects on co-morbid diseases (9). Obesity surgery also provides a novel methodological approach for studying whether specific brain-level differences between obese and lean individuals are causes or consequences of obesity. A longitudinal study on individuals undergoing obesity surgery allows us to assess whether the observed differences between obese and lean individuals are associated with the obese phenotype and are thus recoverable by the surgery, or whether they represent stable individual differences that constitute as risk factors which explain why some people become obese or addicted. Such dissociation has a major impact on the appropriate psychological and pharmacological treatment of obesity.

### 2.5. Positron Emission Tomography (PET) and tracers

Positron emission tomography (PET) combined with 14(R, S)-[F]-fluoro-6-thia-heptadecanoid acid ([F]FTHA) with PET is used to measure free fatty acid uptake and oxidation in myocardium and skeletal muscle (73). [F]FTHA is metabolically trapped tracer. 89% [F]FTHA taken up by the heart enters mitochondria and the rate of radioactivity accumulation of [F]FTHA reflects the  $\beta$ -oxidation in the heart (74). 36% of the [F]FTHA accumulated in skeletal muscle, enters mitochondria suggesting that in skeletal muscle [F]FTHA traces FFA uptake but not specifically FFA beta-oxidation(74). By using simple graphical analysis (75) the free fatty acid uptake rates in the tissue can be calculated.

In addition to its role in studying tissue metabolism and blood flow, PET can also be used to study specific neurotransmitters in the brain. In this study, we will focus on two such neurotransmitter systems, dopamine and opioid, given their prominent role in reward functions in humans and previous preclinical evidence suggesting that they are implicated in obesity. Striatal and thalamic dopamine D2 receptors are measured with the antagonist [C]raclopride, which is probably the best validated PET neuroreceptor radioligand (76). On the other hand,  $\mu$ -opioid receptors can be measured with the high-affinity agonist radioligand [C]carfentanil, which is also well validated for human studies (77). These receptors are found throughout the brain, with the exception of the occipital cortex. Both radioligands can be quantified without arterial blood samples, using a simple reference tissue method (cerebellum for [C]raclopride and occipital cortex for [C]carfentanil.

## **3. OBJECTIVES AND HYPOTHESES**

## 3.1. Objectives:

The objectives of this study are to measure effect of weight loss and the possible differences between sleeve gastrectomy and gastric bypass:

- 1. On whole-body and fasting free fatty acid metabolism in myocardium, skeletal muscle, liver, pancreas, intestine, bone, brain and subcutaneous and visceral fat.
- 2. On total body fat and abdominal fat distribution & abdominal fat volumes
- 3. On liver fat content
- 4. On glycemic control and on biochemical markers (leptin, ghrelin, adiponectin, HDL, LDL, triglycerides, cholesterol, calcium, B12-vitamin, cytokines, bile acids and high sensitivity C-reactive protein).
- 5. On brain white and gray matter volumes and distribution
- 6. On brain activation response to food stimuli before and after surgery
- 7. On the two specific neurotransmitter systems, dopamine and opioid
- 8. On correlation between brain activation to food stimuli and hormonal changes especially of the gastrointestinal peptides (e.g. ghrelin)
- 9. On correlation between the subjective feelings of hunger and brain activation
- **10.** On markers of bone metabolism (Vitamin D, PTH, S-Ctx, bsAP, PINP and osteocalcin) and bone mineral density
- 11. On quantitative and metabolic changes in the bone marrow fat

We also aim:

- **12.** To take DNA samples for further investigation on genetic markers related to cardiovascular diseases, type 2 diabetes and obesity risk factors as a part of CMGene-study
- 13. To investigate the effect of morbid obesity on the histology and thus take biopsies
  - a. During endoscopy from gastric mucus, duodenum, antrum and corpus
    - b. During surgery from liver, abdominal subcutaneous and visceral fat
- **11.** To investigate the effect of morbid obesity and the surgery-induced weight loss on the histology of abdominal subcutaneous adipose tissue by taking a biopsy from abdominal adipose tissue
- 12. To measure the effects of bariatric surgery on gene and protein expression in these tissue biopsies
- 13. To compare the general risk factors between sleeve gastrectomy (SG) and gastric bypass
- 14. To obtain information about the hormonal benefits and long-term results of SG
- 15. To investigate the effects of bariatric surgery on intestinal perfusion and metabolism.
- **16.** To investigate the effects of bariatric surgery on the rate of bone turnover and bone quality using paired bone biopsies
- **17.** The rate of bone turnover (bone biopsy),

## 3.2. Hypotheses:

3.2.1. The main hypotheses of the PET study with [18F]FTHA is that the free fatty acid uptake among obese in the brain, heart, pancreas, liver, intestine, skeletal muscles, abdominal fat tissue and in the bone is increased and then decreased after weight loss.

### 3.2.2. The main hypotheses of MRI/MRS

We predict that the liver and mediastinal fat content is effectively decreased due to surgery.

Brain white matter volumes among obese are expected to be larger and to decrease during surgeryinduced weight loss. The bone marrow fat content should decrease upon surgery induced weight loss.

3.2.3. The main hypotheses of the brain activation studies (fMRI) and molecular imaging studies (neurotransmitter PET):

We predict that the neural responses of the reward circuit (amygdale, ventral striatal and midbrain regions) will be decreased post-operatively for the appetizing vs. bland foods in surgical groups. The differential activity is expected to be more profound in the patient group before surgery vs. healthy controls [54]. This between-groups difference in the activity of the reward system is expected to diminish in the post-operative scan. Furthermore, it is expected that this change in responsiveness is due to decreased responses to appetizing food only. In addition the changes of brain activation due to surgery-induced weight loss are expected to correlate with changes in gastrointestinal hormone secretion and with subjective feelings of hunger. Obesity is predicted to be associated with lowered grey and white matter volume (as measured by voxel-based morphometry), as well as altered connectivity between the subcomponents of the reward circuit (as measured by diffusion tensor imaging).

We predict that striatal  $D_2$  receptors, as measured with [C]raclopride, are decreased in obese individuals in comparison with lean control subject, and that weight loss following surgery results in increase in the number of these receptors. This would be consistent with lowered sensitivity to actual food reward in obesity. These receptors are also expected to predict functional responses in fMRI, especially receptors in the ventral striatum. Given the role of  $\mu$ -opioid receptors in reward functions, we predict that these receptors are increased in the brain reward network in obesity, consistent with hypersensitivity to anticipatory reward in obesity. Again, these receptors are hypothesized to correlate with fMRI responses – and with dopamine  $D_2$  receptors. Finally, we predict that weight loss will normalize the brain opioid dysfunction in obesity.

## 3.2.4. The main hypothesis of the bone biopsy and bone mineral density studies

We hypothesize that surgery-induced weight loss leads to increased rate of bone turnover where the balance is tilted towards increased bone resorption. This could result in decreased bone mass.

## 4. STUDY DESIGN

## 4.1. Study type

The study is a prospective, randomised study.

## 4.2. Study design

Patient Group (will be studied pre and 6 months after the surgery):

Visits before Surgery	Examinations (table 1 and table 2 in the laboratory test)
Preliminary visit	Doctor's checkup Oral glucose tolerance test Visit to the PET and MRI scan
1. PET-visit	Calorimetry (fasting) Perfusion-PET PET-scan with 18F-FTHA -tracer
2. PET-visit MRI-visit	PET-scan with 11C-raclopride ja 11C-carfentanil tracers MRI-scan

Visits after Surgery	Examinations
Preliminary visit	Oral glucose tolerance test
1. PET-visit	Calorimetry (fasting) Perfusion-PET PET-scan with 18F-FTHA -tracer
2. PET-visit	PET-scan with 11C-raclopride and 11C-carfentanil tracers
MRI-visit	MRI-scan

Control group (will be studied only once expect brain fMRI):

Visit times	Examinations
Preliminary visit	Doctor's checkup Oral glucose tolerance test Blood samples
1. PET-scan	Calorimetry (fasting) Perfusion-PET PET-scan with 18F-FTHA -tracer
2. PET-visit	PET-scan with 11C-raclopride and 11C-carfentanil tracers
1. MRI-visit	MRI-scan
2. MRI-visit (after 6 months)	MRI-scan

## 5. PATIENT/SUBJECT SELECTION

## 5.1 Source population

The study consists totally of 60 study subjects. Of these 40 are morbidly obese adults (male of female,  $BMI \ge 40 \text{ kg/m}^2$  or if there is additional risk factor  $BMI \ge 35 \text{ kg/m}^2$ ) and they will be recruited from patients undergoing the surgical procedure as a part of normal treatment mode. The morbidly obese patients are randomized either for laparoscopic sleeve gastrectomy (n=20) or Roux-en-Y gastric bypass (n=20). For a control group 20 lean, healthy, age and sex matched subjects will

be recruited. The control subjects will be recruited according to personal contacts, electrical and traditional bulletin boards, and newspaper advertisements.

## 5.2 Inclusion and exclusion criteria

#### Inclusion criteria for the patient population

1) BMI > 40 kg/m^2 or  $\ge$  35 if there is an additional risk factor (lean control group BMI 18-27 kg/m^2)

2) Age: 18-60 years

3) Previous, carefully planned, conservative treatments for obesity have failed

#### Exclusion criteria for the patient population

- 1) BMI over 60 kg/m^2
- 2) Weight more than 170 kg
- 3) Waist circumference > 150 cm
- 4) Mental disorder or poor compliance
- 5) Eating disorder or excessive use of alcohol
- 6) Active ulcus-disease
- 7) Diabetes requiring insulin treatment or fasting glucose more than 7 mmol/l
- 8) Pregnancy
- 9) Past dose of radiation
- 10) Presence of any ferromagnetic objects that would make MR imaging contraindicated

11) Any other condition that in the opinion of the investigator could create a hazard to the subject safety, endanger the study procedures or interfere with the interpretation of study results

#### Inclusion criteria for the control group

- 1) BMI 18-27 kg/m2
- 2) Age 18-60 years
- 3) Fasting plasma glucose less than 6.1 mmol/l
- 4) Normal glucose tolerance test (OGTT)

#### Exclusion criteria for the control group

- 1) Blood pressure > 140/90 mmHg
- 2) Any chronic disease
- 3) Mental disorder or poor compliance
- 4) Any chronic medical defect or injury which hinder/interfere everyday life
- 5) Eating disorder or excessive use of alcohol
- 6) Pregnancy
- 7) Past dose of radiation

8) Any other condition that in the opinion of the investigator could create a hazard to the subject safety, endanger the study procedures or interfere with the interpretation of study results

9) Presence of any ferromagnetic objects that would make MR imaging contraindicated

## 6. ASSESSMENTS

## 6.1 General study outline

**Patient Group:** (will be studied pre and 6 months after the surgery):

Visits before Surgery	Examinations
Preliminary visit	Doctor's checkup
	Oral glucose tolerance test
	Visit to the PET and MRI scan
1. PET-visit	Calarimetry (fasting)
	Perfusion-PET
	PET-scan with 18F-FTHA -tracer
2. PET-visit	PET-scan with 11C-raclopride and 11C-carfentanil tracer
MRI-visit	MRI-scan

Visits after Surgery	Examinations
Preliminary visit	Oral glucose tolerance test
1. PET-visit	Calorimetry (fasting) Perfusion-PET PET-scan with 18F-FTHA -tracer
2. PET-visit	PET-scan with 11C-raclopride and 11C-carfentanil tracer
MRI-visit	MRI-scan

Control group: (will be studied only once):

Visit times	Examinations
Preliminary visit	Doctor's checkup
	Oral glucose tolerance test
	Blood samples
1. PET-scan	Calorimetry (fasting)
	Perfusion-PET
	PET-scan with 18F-FTHA -tracer
2. PET-visit	PET-scan with 11C-raclopride ja 11C-carfentanil tracer
1. MRI-visit	MRI-scan
2. MRI-visit (after 6 months)	MRI-scan

### Pre-operative studies in the surgery policlinic

The history of carefully planned, conservative treatments for obesity is assessed when patients seeking surgical treatment come in policlinic. A possible endocrinolocigal disease is excluded by the endocrinologist. Eating disorder is excluded by dietician using eating questionnaires BES and BITE. In addition to ECG the following laboratory values are measured pre-operatively: CBC (complete blood count), TSH, urate, fasting plasma glucose, GHbA1c, INR (blood coagulation), albumin, ALAT, AFOS, GT, total cholesterol, HDL, LDL, TG, creatine, Na, K, Ca, Pi, B12, D25,

folate, hs-CRP, plasma cytokines, IL1 $\beta$ , adiponectin, leptin, bile acids, gastrointestinal peptides (CCK, bombesin, gastrin-releasing peptide, GIP, GLP1, peripheral PYY, pancreatic polypeptide, oxyntomodulin, ghrelin, obestatin), lipoprotein fractions, serum fatty acid composition, non-cholesterol sterols (squalene, cholestenol, desmosterol, lathosterol, campesterol, sitosterol, cholestanol, avenasterol) and the sizes of LDL - & HDL-particles. In addition oral glucose tolerance test (OGTT) of 75 g with insulin, fatty acid and c-peptide measurements (time points 0 and 120 minutes) and dexamethasone test of 1 mg, are done.

Pre-operative gastroscopy is performed to all patients in the policlinic of surgery. During gastrointestinal endoscopy routine biopsies are taken from duodenum, antrum and corpus. This visit includes the decision if the patient is eligible for surgery. If the patient is accepted, the surgical risk factors and the study information are carefully explained. Randomisation either in the gastric sleeve or gastric bypass group is done using closed envelopes. Pre-operative quality of life is assessed using BAROS-survey.

After this, selected patients will visit the dietician. The dietician gives first instructions about the pre-operative very-low-calorie-diet (VLCD) phase and second nutritional advice about the post-operative phase. During the VLCD-phase patients usually lose weight approximately about 1.5-2.5 kg in a week. Before the surgery an abdominal ultrasound is performed to exclude gallstones. If gallstones are found, they are removed during the bariatric surgery.

### 6.2 PET studies

Pre operative PET studies will be performed before the preoperative VLCD phase (see chapter 6.1). PET studies are done in two separate PET visits both after a 10-12 hour overnight fast. In the first PET visit calorimetry measurements (see chapter 6.5), perfusion of intestine using [O]H2O and tissue (brain, heart, liver, pancreas, intestine, abdominal subcutaneous and visceral fat, bone and skeletal muscle) FFA uptake with [F]FTHA PET will be studied. In the other PET visit brain striatal D2R density will be measured with radioligand [C]raclopride (78) and brain MOR density using [C]carfentanil (79). In both PET visits two catheters are inserted, one in an antecubital vein for injection of tracers and another in the opposite antecubital arteliazed vein for blood sampling. The subjects will be lying in a supine position throughout the studies.

The PET visit 1 PET studies start with myocardial perfusion measurements at rest. For the measurement of myocardial blood flow, 900 MBq of [O]-H2O will be injected intravenously and a dynamic scan will be performed for 6 min. Then injection of [F]FTHA (185 MBq) is given and dynamic PET scanning starts with brain (40 min) and follows with heart/bone (20 min), liver/pancreas (20 min), abdominal area/intestine (20 min), and finally skeletal muscle/bone (10min, static) scan is performed. Radiotracers [O]H2O (80) and [F]-FTHA(81) (73) are produced and myocardial perfusion (82)(83) and FFA uptake (75) in different tissues analysed as previously described. Plasma radioactivity is measured with an automatic gamma counter (Wizard 1480 3", Wallac, Turku, Finland). Plasma glucose and free fatty acids are frequently measured during the PET study.

The PET visit 2 studies start with the injection of  $[^{11}C]$ raclopride (300 MBq) and dynamic brain scanning will be performed for 51min Receptor binding will be assessed as the binding potential (BPND), which is the ratio at equilibrium of specific binding to non-displaceable binding in the brain, using cerebellum as the reference region. 100 min after  $[^{11}C]$ raclopride injection the injection of  $[^{11}C]$ carfentanil (300 MBq) will be given and dynamic brain scanning performed for 60min. Receptor binding will be assessed as the binding potential (BPND), using the occipital cortex as the

reference region. Both ROI-based statistics and statistical parametric mapping (SPM) (84) will be used in the statistical analyses.

An integrated PET/CT, GE DiscoveryTM ST System (General Electric Medical Systems, Milwaukee, WI, USA) with resolution of 3.75 is used for PET studies. All data will be corrected for dead-time, decay and measured photon attenuation. Dynamic PET-scans will be reconstructed with MRP reconstruction method (85). Brain scan is performed with a covering the whole brain in 3D mode. CT scans will be conducted to correct for photon attenuation and to evaluate fat masses and tissue density(86) . Plasma radioactivity is measured with an automatic gamma counter (Wizard 1480 3", Wallac, Turku, Finland. Plasma glucose and free fatty acids are frequently measured during the PET study.

According to the study protocol the patients will get two FTHA, two raclopride and two carfentanil injections. These will result in 14.8 mSv of radiation dose. Moreover, the measurement from CT will result in 6.7 mSv of effective dose. Altogether the radiation dose to study subjects will be 22,5 mSv which equals to exposure to natural background radiation in Finland for 4 years and 4 months. Dosimetry calculations done by the hospital physicist can be found from the appendix. So in general, the total dose accounting all PET-studies for patients is less than 22.5 mSv and for control group less than 11.25 mSv.

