## 11. DATA ANALYSIS

## 11.1. Analysis of PET-data

For calculation of skeletal muscle, myocardial, liver, pancreas, and adipose tissue FFA uptake the three compartment model (110) and graphical analysis (75) are employed. Plasma and tissue time-activity curves are analysed graphically to quantify the fractional rate of the tracer transport, KI (73).

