## TUTKIMUSKOODI:

Tutkimusprojektin aikana tutkimushenkilölle aiheutuu säteilyaltistusta seuraavista PET-merkkiaineista.

Merkkiaine	Injisoitava tai inhaloitava aktiivisuus (MBq)	Efektiivinen annos (mSv/MBq)	Keskimääräinen efektiivinen annos injektiota kohti (mSv)
 O-H 2 O	900 MBq	0,0011 mSv/MBq	1,0 mSv
 F-FTHA	185 MBq	0,019 mSv/MBq	3,5 mSv
 C-raklopriidi 300 MBg		0,0067 mSv/MBq	2,0 mSv
 C-karfentaniili 300 MBq		0,0046 mSv/MBq	1,4 mSv

Tutkimussuunnitelman mukaisesti tutkittavalle annetaan yksi (2)  O-H2O, kaksi (2)  F-FTHA, kaksi (2)  C-raklopriidi ja kaksi (2)  C-karfentaniili injektiota. Tästä aiheutuva säderasitus on 14,8 mSv. Lisäksi tutkittavasta mitataan vaimennuskerroin tietokonetomografia mittauksella iteratiivisella rekonstruktiomenetelmällä aivoista kuusi kertaa ja neljästä eri kehon alueesta (rintakehä, vatsa, alavatsa, reidet) kaksi kertaa ja niistä aiheutuu arviolta 6,7 mSv efektiivinen annos. Yhteensä tutkimuksesta aiheutuu 22,5 mSv säderasitus, joka vastaa noin neljän vuoden neljän kuukauden aikana saatua taustasäteilyn määrää Suomessa.

Tämä arvio sisältää  O-H2O,  F-FTHA,  C-raklopriidi ja  C-karfentaniiliinjektioista sekä aivojen, rintakehän, vatsan, alavatsan ja luurankolihaksen alueen vaimennus-korjausmittausten aiheuttaman säderasituksen.

Vertailuarvoja tutkimuksesta aiheutuvalle säteilyann	okselle:
Vuotuinen taustasäteily Suomessa	4 – 5 mSv.
Keskimääräinen efektiivinen annos tutkimus	ta kohti
Vatsan TT-tutkimuksesta	12 mSv.
Pään TT-tutkimuksesta	1.3 mSv.
Luuston gammakuvauksesta (99mTc)	3.7 mSv.
Aivojen SPECT (99mTc)	6.9 mSv.
Sydänlihasperfuusion SPECT (99mTc)	9.1 mSv.
FDG-PET tutkimus	5 mSv.

Kirjallisuusviitteet

Vertailuarvot muista lääketieteellisistä säteilylle altistumisista: Lääketieteellinen aikakauskirja Duodecim 2000;116:664-669.

Annals of the ICRP Pub 106, Radiation dose to patients from radiopharmaceuticals, Vol.38, No 1-2, Pergamon 2008.

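### At PET visit 1 the water scan is assigned to two different organs, skeletal muscle Ki cannot be estimated from its single static frame, and the stated dose subtotals do not add up to the stated total

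*Protocol*

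**What the plan says.** **Water scan.** Objective 15 (Protocol 3.1) reads "To investigate the effects of bariatric surgery on intestinal perfusion and metabolism". The first paragraph of 6.2 includes "perfusion of intestine using" 15O-water in PET visit 1. The second paragraph then gives the order of events: "The PET visit 1 PET studies start with myocardial perfusion measurements at rest". It describes one 900 MBq water injection, given to measure blood flow in the heart, and one 6-minute dynamic scan. The only perfusion analysis it refers to is myocardial. The visit tables in 4.2 and 6.1 list a perfusion PET without naming an organ.

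**Muscle.** The FTHA sequence in 6.2 runs brain 40 min, heart/bone 20 min, liver/pancreas 20 min, abdomen/intestine 20 min, "and finally skeletal muscle/bone (10min, static) scan is performed". Section 11.1 states "For calculation of skeletal muscle, myocardial, liver, pancreas, and adipose tissue FFA uptake the three compartment model" and graphical analysis, and then says that plasma and tissue time-activity curves are analysed graphically to give Ki.

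**Dose.** Section 6.2 counts two FTHA, two raclopride and two carfentanil injections per patient and no water: "These will result in 14.8 mSv of radiation dose". It adds 6.7 mSv for CT and concludes "Altogether the radiation dose to study subjects will be 22,5 mSv", with 11.25 mSv as the limit for controls. Appendix 4 repeats the tracer subtotal ("Tästä aiheutuva säderasitus on 14,8 mSv"), the 6.7 and the 22.5. It gives the number of water injections as the Finnish word for one followed by the digit 2 in brackets.

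**The concern.** Each part is a place where the Protocol, followed as written, does not deliver what it states elsewhere.

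- Someone carrying out the second paragraph of 6.2 would acquire and analyse heart perfusion. Objective 15 would then have no planned perfusion measurement behind it.
- Muscle fatty acid uptake is a named part of the hypothesis in 3.2.1. The method stated for it needs a curve, and the acquisition supplies one point. Whoever analyses the data must choose another estimator afterwards, with no rule fixed in the Protocol.
- The radiation figures are the basis of the exposure statement in 9.1. A subtotal, an injection list and a total that disagree leave it unclear how many water injections were counted.

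The first and third parts are linked: both depend on one unambiguous statement of what the water scan is for and how often it is done.

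**Working it through.** **1. Water scan: the passages side by side**

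| Place | Organ for the water scan |
|---|---|
| 3.1, objective 15 | intestine |
| 6.2, first paragraph | intestine |
| 6.2, second paragraph, acquisition | myocardium |
| 6.2, second paragraph, analysis | myocardium |
| 4.2 and 6.1, visit tables | not stated |

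There is one injection and one scan per visit 1, and two organs are named for it. No intestinal acquisition or intestinal perfusion analysis is described.

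**2. Muscle: what one frame can identify**

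Timing, assuming that the scans run back to back from injection: 40 + 20 + 20 + 20 = 100, so muscle is imaged at about 100 to 110 min.

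The graphical model, with tissue activity C_T, plasma activity C_p and P(t) the integral of C_p from 0 to t, is

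C_T(t)/C_p(t) = Ki × P(t)/C_p(t) + V0.

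Each frame gives one such equation. The unknowns are Ki (slope) and V0 (intercept). One static frame gives a design matrix of rank 1 for two unknowns, so the slope is not identified. A compartment fit has more unknowns still. Several late frames give rank 2, so the slope can be estimated for tissues with dynamic late scans.

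From one frame at time T, together with the plasma curve, one can compute

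FUR = C_T(T)/P(T) = Ki + V0 × C_p(T)/P(T).

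FUR equals Ki only if the last term is negligible.

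**3. Dose: reproducing the stated figures**

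Per-injection doses from Appendix 4:

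- water: 900 × 0.0011 = 0.99 mSv
- FTHA: 185 × 0.019 = 3.515 mSv
- raclopride: 300 × 0.0067 = 2.01 mSv
- carfentanil: 300 × 0.0046 = 1.38 mSv

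Two each of the last three: 2 × (3.515 + 2.01 + 1.38) = 13.81 mSv. Adding water and then CT at 6.7 mSv:

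| Water injections per patient | Tracers (mSv) | With CT (mSv) |
|---|---|---|
| 0 (the list in 6.2) | 13.81 | 20.51 |
| 1 | 14.80 | 21.50 |
| 2 (one per visit 1, two such visits) | 15.79 | 22.49 |

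The printed parts give 14.8 + 6.7 = 21.5, which is 1.0 mSv below the printed total. That gap is one water injection. The subtotal of 14.8 corresponds to one water injection and the total of 22.5 to two. The body text lists none. For a control, studied once by PET, half of 22.49 is 11.245, in line with the stated 11.25.

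The background comparison in 6.2 and Appendix 4 (4 years 4 months, or 4.33 years) implies 22.5/4.33 = 5.2 mSv a year, against 21.5/4.33 = 5.0. Appendix 4 gives annual background as 4 to 5 mSv, so this comparison fits 21.5 better and should be recalculated along with the rest.

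**The case against.** The strongest reply is that these are wording slips and no design failure. Four points in it carry weight.

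- **Organ.** A reader might infer that objective 15 is bound to have no perfusion data, or that it needs injections beyond the stated dose. Neither follows. One of the two paragraphs may simply name the wrong organ, and correcting that need not change the number of injections. Nor is it shown that the cardiac scan misses the bowel, since the Protocol gives no axial field of view or bed position for it. What stands is that no intestinal acquisition or analysis is described.
- **Dose.** A reader might infer that patients receive more than the 22.5 mSv stated. The described sequence reproduces 22.5 and 11.25. A second water injection per visit would bring these to 22.5 + 2 × 1.0 = 24.5 mSv and 11.25 + 1.0 = 12.25 mSv with CT unchanged, but no passage plans one. The disagreement among subtotal, injection list and count stands.
- **Other tissues.** A reader might infer that no tissue in 11.1 can be analysed as stated, because only the brain is scanned from injection and it is not listed there. Graphical analysis does not need early tissue frames; late dynamic frames with a full plasma curve suffice. Section 2.5 speaks of simple graphical analysis, and 6.2 cites only the graphical method for fatty acid uptake, so the compartment model is plausibly its theoretical basis and not a separate fit. The text should say so.
- **Muscle.** A reader might infer that muscle uptake cannot be obtained at all. It can, by a one-frame uptake rate, because plasma radioactivity is measured. It might be said that naming the estimator belongs in an analysis plan. But 11.1 does not leave it open: it states a method that the planned muscle scan cannot support.

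A call for FUR in every tissue would also go too far. Hypothesis 3.2.1 compares obese with lean, and before with after, within each tissue.

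**Conclusion.** The point holds in three limited parts.

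1. The Protocol contradicts itself on the target of the single water scan in visit 1. As described, no intestinal perfusion measurement is planned for objective 15.
2. Skeletal muscle Ki cannot be estimated by the method in 11.1, because one static frame does not determine a slope. This rests on the static scan in 6.2 being the only muscle acquisition, which is all the Protocol describes. The 100 to 110 min timing assumes back-to-back scans, but the conclusion does not depend on it.
3. The stated dose parts fall 1.0 mSv short of the stated total. The total agrees with the described sequence and the appendix coefficients; the 14.8 subtotal, the list without water and the appendix's one-or-two count do not agree with it. No understatement of the described exposure is shown.

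The consequences are moderate: one secondary objective without a described measurement, one tissue in a main hypothesis with an unworkable estimator, and dose paperwork that does not add up.

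**What to change.** - **Water scan.** Reconcile objective 15 and the two paragraphs of 6.2 on which organ is imaged, and name the matching perfusion analysis. If this changes the number of injections, recompute the dose totals in 6.2, 9.1 and Appendix 4. Otherwise, if the intestine is not imaged, remove intestinal perfusion from objective 15.
- **Muscle.** In 11.1, state that skeletal muscle uptake is computed as a fractional uptake rate, tissue activity divided by the plasma integral. Label it FUR and not Ki, and use it in the same way before and after surgery and between groups. The small downside is the assumption of a negligible intercept, which means that muscle values are not directly comparable with graphical Ki in other tissues.
- **Other tissues.** Keep the graphical method where late dynamic frames exist, and say that no full compartment fit is intended for tissues not scanned from injection.
- **Dose.** Bring the tracer subtotal, the injection list in 6.2, the water count in Appendix 4 and the background comparison into agreement with one stated count and with the total.

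Cost: edits to three sections and the appendix, a rechecked dose table, and notification of the ethics committee. FUR uses data already planned.
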